8.1.3. Tertiary Efficacy Parameters: Patient Centered Outcome Assessments (PCOAs)

The PCOAs consist of PRO assessments which will be implemented using sponsor-provided ePRO devices. Participants will complete specific PRO assessments based on their site country location as described in the SoA for the applicable cohort (see SoA for Cohorts 1 and 2, and SoA for Cohort 3) and Table 5.

Table 5. Patient Reported Outcome Measures

| Measure | Frequency | Number of Questions | Estimated Completion Time | US Sites Only ^a | Ex-US Sites ^b |
|--|--|------------------------|---------------------------------|---|-----------------------------|
| Eating-Related Factors Daily Diary ^c | Cohorts 1, 2 and 3: Daily, starting at V2 (Pbo run-in) to End of Treatment | 5 | 2 minutes | At home, (handheld device) | |
| PGI-S | Cohorts 1, 2 and 3: At each planned inclinic study visit, starting at V2 (Pbo run-in) to End of Treatment | 4 | 1 minute | At the clinic (electronic tablet) | N/A |
| PGI-C | Cohorts 1 and 2: V5 (Week 4) V10 (Week 16) V13 (Week 26) Cohort 3: V5 (Week 4) V11 (Week 16) V15 (Week 24) V19 (Week 32) | 4 | 1 minute | | |
| PROMIS® Fatigue Custom 9-item | Cohorts 1 and 2: V2 (Pbo run-in) V3 (Day 1) V10 (Week 16) V13 (Week 26) Cohort 3: V2 (Pbo run-in) V3 (Day 1) V11 (Week 16) V15 (Week 24) V19 (Week 32) | 9 | 11 minutes | | |
| PROMIS® Physical Function Custom 13-item | Cohorts 1 and 2: V2 (Pbo run-in) V3 (Day 1) V10 (Week 16) V13 (Week 26) Cohort 3: V2 (Pbo run-in) V3 (Day 1) V11 (Week 16) V15 (Week 24) V19 (Week 32) | 13 | | | |

| Measure | Frequency | Number of Questions | Estimated Completion Time | US Sites Only ^a | Ex-US Sites ^b |
|----------------------------|--|------------------------|---------------------------------|---|-----------------------------------|
| IWQOL-Lite-CT [©] | Cohorts 1 and 2: V2 (Pbo run-in) V3 (Day 1) V10 (Week 16) V13 (Week 26) Cohort 3: V2 (Pbo run-in) V3 (Day 1) V11 (Week 16) V15 (Week 24) V19 (Week 32) | 20 | | | |
| SF-36v2® | Cohorts 1 and 2: V2 (Pbo run-in) V3 (Day 1) V10 (Week 16) V13 (Week 26) Cohort 3: V2 (Pbo run-in) V3 (Day 1) V11 (Week 16) V15 (Week 24) V19 (Week 32) | 36 | 9 minutes | At the clinic (electronic tablet) | At the clinic (electronic tablet) |

- a. Participants from US sites will complete all PRO assessments.
- b. Participants from ex-US sites will complete only the SF-36v2[®].
- c. Participants from selected US sites will complete the Eating-Related Factors Daily Diary.

Every effort should be made to have the participant complete all PRO assessments as per the SoA for the applicable cohort (see SoA for Cohorts 1 and 2, and SoA for Cohort 3). Site-based PRO assessments should be completed by the participant at the beginning of the visit before any medical procedures or interactions with the medical staff (as much as practically possible) take place.

Additional details regarding the process of administration of the PROs will be provided in a study-specific user manual supplied by the sponsor.

8.1.3.1. Eating-Related Factors Daily Diary

The Eating-Related Factors Daily Diary is a daily, self-administered questionnaire that measures eating-related factors. The diary consists of 5 items that ask participants to evaluate their hunger, appetite, fullness, and cravings in the past 24 hours.

8.1.3.2. Patient's Global Impression of Severity (PGI-S)

The PGI-S is a supportive item recommended by FDA for use as an anchor measure to generate an appropriate threshold that represents meaningful within-patient change in the target patient population. There are 4 PGI-S items that ask participants to evaluate the severity of their hunger, appetite, fullness, and cravings in the past 7 days.

8.1.3.3. Patient's Global Impression of Change (PGI-C)

The PGI-C is a supportive item recommended by FDA for use as an anchor measure to generate an appropriate threshold that represents meaningful within-patient change in the target patient population. There are 4 PGI-C items that ask participants to rate the overall change in their hunger, appetite, fullness, and cravings since they started taking the study medication.

8.1.3.4. PROMIS® Fatigue Custom 9-item Version

The PROMIS® Fatigue²⁹ Custom 9-item Version is a self-reported measure that assesses a range of symptoms in the past 7 days from mild subjective feelings of tiredness to an overwhelming, debilitating, and sustained sense of exhaustion that likely decreases one's ability to execute daily activities and function normally in family or social roles. A global raw score ranging from 9 to 45 is calculated and can be translated into a T-score (Mean=50, SD=10) using the applicable score conversion table or online HealthMeasures Scoring Service,³⁰ where full derivation details will be provided in the SAP.

8.1.3.5. PROMIS® Physical Function Custom 13-item Version

The PROMIS® Physical Function³¹ Custom 13-item Version is a self-reported measure that assesses capability rather than actual performance of physical activities. It includes assessment of one's ability to walk, climb stairs, run/jog, exercise as well as instrumental activities of daily living. A global raw score ranging from 13 to 65 is calculated and can be translated into a T-score (Mean=50, SD=10) using the applicable score conversion table or online HealthMeasures Scoring Service,³⁰ where full derivation details will be provided in the SAP.

8.1.3.6. Impact of Weight on Quality of Life-Lite (IWQOL-Lite) Clinical Trials Version

The IWQOL-Lite-CT^{©32} was developed for use in the context of clinical trials for obesity, with 20 items addressing concerns that are specifically relevant to the study population.

8.1.3.7. SF-36v2® Health Survey

The SF-36v2^{®33} is a 36-item questionnaire that measures functional health and well-being from a patient's perspective. It is a generic questionnaire and can be used across age (adults), disease, and treatment groups. The questionnaire consists of 8 health domain scales: physical functioning (10 items), role-physical (4 items), bodily pain (2 items), general health (5 items), vitality (4 items), social functioning (2 items), role-emotional (3 items), mental health (5 items), reported health transition (1 item) and 2, physical and mental component summary scores. Each health domain scale raw score is transformed to 0-100 scale which can then be converted to norm-based T-scores (Mean=50, SD=10) using scoring software provided by the developer, where full derivation details will be provided in the SAP.

8.2. Safety Assessments

Planned time points for all safety assessments are provided in the SoA for the applicable cohort (see SoA for Cohorts 1 and 2, and SoA for Cohort 3). Unscheduled clinical laboratory measurements may be obtained at any time during the study to assess any perceived safety issues.

8.2.1. Physical Examinations

Physical examinations are performed as indicated in the SoA for the applicable cohort (see SoA for Cohorts 1 and 2, and SoA for Cohort 3).

Physical examinations may be conducted by a physician, trained physician's assistant or nurse practitioner as acceptable and according to local regulation. A complete physical examination will include, at a minimum, assessments of the participant's general appearance, head, ears, eyes, nose, mouth, throat, neck (including thyroid examination), skin, heart and lung examinations, lymph nodes, as well as gastrointestinal, musculoskeletal and neurological systems.

Height will be measured after the participant has removed their shoes and will be collected at V1 only.

A limited physical examination is performed at the in-clinic follow-up visit and may be performed at non-specified visits if there are findings during the previous physical examination or new/open AEs, if appropriate and at investigator discretion. The limited physical examination will be focused on general appearance, lungs, heart, and participant reported symptoms.

Investigators should pay special attention to clinical signs related to previous serious illnesses.

8.2.2. Vital Signs

8.2.2.1. Blood Pressure and Pulse Rate

In this study, assessment of vital signs (systolic BP, diastolic BP, and pulse rate) will occur at the nominal time points specified in the SoA for the applicable cohort (see SoA for Cohorts 1 and 2, and SoA for Cohort 3) per the following specifications:

- At V1, the participant's arm circumference should be measured (eg, using an anthropometric tape) at the midpoint of the length of the upper arm and the appropriate cuff selected and used throughout the study.
- BP and pulse rate will be measured via an automated device using an oscillometric method (not auscultation).

- Assessment of BP and pulse rate can be manual (rather than using an automated device), only if an automated device is not available; however, when done manually pulse rate must be measured in the brachial/radial artery for at least 30 seconds.
- Supine BP and pulse rate will be measured with the participant's arm supported at the level of the heart, following a rest of at least 5 minutes and BP will be recorded to the nearest mm Hg. Triplicate assessments will be measured, with an interval of at least 1-2 minutes between each measurement, and these will be performed pre-dose (as applicable) at each planned in-clinic study visit. For visits with post-dose PK collections as specified in the SoA for the applicable cohort (see SoA for Cohorts 1 and 2, and SoA for Cohort 3), these triplicate assessments will also be performed 1 time within the window of approximately 2-6 hours post-dose (around the same time as post-dose PK samples are collected and according to the chronology in Appendix 9). Each triplicate reading will be recorded, and the average of the 3 measurements at V3 (Day 1) will serve as the participant's baseline.
- Same arm (preferably the dominant arm) will be used for BP and pulse rate assessments throughout the study, whenever possible.
- Participants should be instructed not to speak during BP and pulse rate measurements.
- See Appendix 9 for proposed chronology of procedures for nominal time points when vital sign assessments coincide with other procedures.

Additional collection times, or changes to collection times of BP and pulse rate will be permitted, as necessary, to ensure appropriate collection of safety data.

8.2.3. Electrocardiograms

Standard 12-lead ECGs should be collected at times specified in the SoA section of this protocol for the applicable cohort (see SoA for Cohorts 1 and 2, and SoA for Cohort 3) using an ECG machine that automatically calculates the HR and measures PR, QT, and QTcF intervals and QRS complex. All scheduled ECGs should be performed after the participant has rested quietly for at least 10 minutes in a supine position, and prior to dosing (as applicable), according to the chronology in Appendix 9.

If a) a post-dose QTcF interval remains ≥ 30 msec from the baseline and is > 450 msec; or b) an absolute QTcF value is ≥ 500 msec for any scheduled ECG for greater than 4 hours (or sooner, at the discretion of the investigator); or c) QTcF intervals get progressively longer, the participant should undergo continuous ECG monitoring (eg, cardiac telemetry or frequent ECG ascertainment as per investigator's medical judgment). A cardiologist should be consulted if QTcF intervals do not return to less than the criteria listed above after 8 hours of monitoring (or sooner, at the discretion of the investigator).

In some cases, it may be appropriate to repeat abnormal ECGs to rule out improper lead placement as contributing to the ECG abnormality. It is important that leads be placed in the same positions each time in order to achieve precise ECG recordings. If a machine-read QTcF value is prolonged, as defined above, repeat measurements may not be necessary if a qualified medical provider's interpretation determines that the QTcF values are in the acceptable range.

ECG values of potential clinical concern are listed in Appendix 7.

8.2.4. Clinical Safety Laboratory Assessments

See Appendix 2 for the list of clinical safety laboratory tests to be performed and the SoA for the applicable cohort (see SoA for Cohorts 1 and 2, and SoA for Cohort 3) for the timing and frequency. All protocol-required laboratory assessments, as defined in Appendix 2, must be conducted in accordance with the laboratory manual and the SoA for the applicable cohort (see SoA for Cohorts 1 and 2, and SoA for Cohort 3). Unscheduled clinical laboratory measurements may be obtained at any time during the study to assess any perceived safety issues.

The investigator must review the laboratory report, document this review, and record any clinically relevant changes occurring during the study in the AE section of the CRF. Clinically significant abnormal laboratory findings are those which are not associated with the underlying disease, unless judged by the investigator to be more severe than expected for the participant's condition.

All laboratory tests with values considered clinically significantly abnormal during participation in the study or within 28 to 35 days after the last dose of study intervention should be repeated until the values return to normal or baseline or are no longer considered clinically significant by the investigator or medical monitor.

If such values do not return to normal/baseline within a period of time judged reasonable by the investigator, the etiology should be identified and the sponsor notified.

See Appendix 6 for suggested actions and follow-up assessments in the event of potential DILI.

8.2.5. Management of Hypoglycemia

While hypoglycemia is not expected in the study participants, FPG will be measured at each clinic visit via the central lab. In addition, as a precaution, participants will be instructed to recognize the signs and symptoms associated with hypoglycemia.

Any episode of hypoglycemia must be captured on the AE CRF with specific details captured on the HAE Form CRF. For the definition of a hypoglycemic episode and severity categorization see Section 8.2.5.1 below.

8.2.5.1. Definition and Severity of Hypoglycemic Adverse Event (HAE)

The investigator must assess the glucose values reported by the central laboratory, as well as any signs or symptoms reported by the study participant.

HAE is defined as one of the following:³⁴

- a. Asymptomatic hypoglycemia: An event not accompanied by typical symptoms of HAE but a glucose value of <70 mg/dL (3.9 mmol/L) using either glucometer (fingerstick blood glucose) at the study site or sponsor-identified central laboratory (plasma glucose).
- b. Documented symptomatic hypoglycemia: An event during which typical symptoms of HAE are accompanied with a glucose value of <70 mg/dL (3.9 mmol/L), using glucometer at the study site or sponsor identified central laboratory, and the clinical picture includes prompt resolution with food intake, subcutaneous glucagon, or IV glucose.
- c. Probable symptomatic hypoglycemia: An event during which symptoms of HAE are not accompanied by a glucose determination but was presumably caused by a glucose concentration of <70 mg/dL (3.9 mmol/L), and the clinical picture includes prompt resolution with food intake, subcutaneous glucagon, or IV glucose.

Each episode of HAE must be categorized with respect to severity. In order to characterize the event as severe, all 3 criteria below must be met:

- 1. The participant was unable to treat him/herself. Neurologic impairment, and not the age of the participant, is the explanation for why the participant could not treat him/herself and required the assistance of another person.
- 2. The participant exhibited at least 1 of the following neurological symptoms:
 - Memory loss;
 - Confusion;
 - Uncontrolled behavior;
 - Irrational behavior;
 - Unusual difficulty in awakening;
 - Suspected seizure;
 - Seizure;
 - Loss of consciousness.

3. Either:

- If blood glucose was measured and was ≤54 mg/dL (2.7 mmol/L) using glucometer (or central laboratory); or
- If blood glucose was not measured, the clinical manifestations were reversed by oral carbohydrates, subcutaneous glucagon, or IV glucose.

Events that do not meet all the criteria above for severe HAE are characterized as mild or moderate in severity.

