- 16. Previous administration with an investigational product (eg, drug or vaccine) within 30 days (or as determined by the local requirement) or 5 half-lives before the first dose of study intervention used in this study, whichever is longer.
- 17. Known prior participation in a trial involving PF-06882961.

Diagnostic Assessments:

- 18. A PHQ-9 score ≥15 obtained at V1, V2 or V3.
- 19. Response of "yes" to question 4 or 5, or on any behavioral question on the C-SSRS at V1, V2 or V3.

- 20. At V1, V2 or V3 prior to randomization, supine BP ≥160 mmHg (systolic) or ≥100 mmHg (diastolic), following at least 5 minutes of supine rest. BP should be measured in triplicate and the average of the 3 BP values should be used to determine the participant's eligibility.
- 21. At V1, V2 or V3 prior to randomization, 12-lead ECG that demonstrates clinically relevant abnormalities that may affect participant safety or interpretation of study results (eg, QTcF interval >450 msec, complete LBBB, signs of an acute or indeterminate-age myocardial infarction, ST-T interval changes suggestive of myocardial ischemia, second- or third-degree AV block, or serious bradyarrhythmias or tachyarrhythmias). If the QTcF exceeds 450 msec, or QRS exceeds 120 msec, the ECG should be repeated 2 more times and the average of the 3 QTcF or QRS values should be used to determine the participant's eligibility. Computer-interpreted ECGs should be overread by a physician experienced in reading ECGs before excluding participants.
- 22. A positive urine drug screen at V1 that is consistent with illicit drug use. Note: Participants who have been medically prescribed medications including but not limited to, opiates/opioids or benzodiazepines and report the use of these drugs to the investigator at V1 may be allowed to participate with notification to the sponsor.
- 23. Participants with ANY of the following abnormalities in clinical laboratory tests at V1, as assessed by the study specific laboratory and confirmed by a single repeat test, if deemed necessary:
 - HbA1c \geq 6.5%;
 - AST or ALT level ≥2 times ULN;
 - TBili level ≥1.5 times ULN;
 - Fasting C-peptide < 0.8 ng/mL;
 - TSH >1.5 times ULN or < LLN;
 - Serum calcitonin > ULN;
 - Amylase or lipase > ULN;
 - FPG \geq 126 mg/dL (7 mmol/L);
 - eGFR <60 mL/min/1.73 m² as calculated by the CKD-EPI equation.

Other Exclusions:

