10.2. Appendix 2: Clinical Laboratory Tests

The following laboratory tests will be performed at times defined in the SoA section of this protocol for the applicable cohort (see SoA for Cohorts 1 and 2, and SoA for Cohort 3). Additional laboratory results may be reported on these samples as a result of the method of analysis or the type of analyzer used by the clinical laboratory, or as derived from calculated values. These additional tests would not require additional collection of blood. Unscheduled clinical laboratory measurements may be obtained at any time during the study to assess any perceived safety issues.

Table 6. Protocol Required Laboratory Assessments

| Hematology | Chemistry | Urine Testing | Other |
|---|---|--|--|
| Hemoglobin Hematocrit RBC count MCV MCH MCHC Platelet count WBC count Total neutrophils (Abs) Eosinophils (Abs) Monocytes (Abs) Basophils (Abs) Lymphocytes (Abs) | BUN Creatinine eGFR Plasma Glucose (fasting) Calcium Sodium Potassium Chloride Total CO ₂ (bicarbonate) AST ALT TBili GGT Alkaline phosphatase Uric acid Albumin Total protein | Urinalysis: pH Glucose (qual) Protein (qual) Blood (qual) Ketones Nitrites Leukocyte esterase Urobilinogen Urine bilirubin Microscopy ^a Urine pregnancy test | HbA1c Plasma insulin (fasting) Serum pregnancy test (β hCG) Lipid panel: • Total cholesterol • Direct LDL-C • HDL-C • Triglycerides TSH Free T4 Calcitonin Amylase Lipase Total bile acids PT/INR/aPTT At V1 only: FSHb C-peptide (fasting) Urine drug screen |
| | Additional Tests (Needed | | |
| | for Hy's Law) AST, ALT (repeat) TBili (repeat) Albumin (repeat) Alkaline phosphatase (repeat) Direct bilirubin Indirect bilirubin CK GGT PT/INR Total bile acids Acetaminophen drug and/or protein adduct levels | | |

- a. Only if urine dipstick is positive for blood, protein, nitrites, or leukocyte esterase.
- b. For female participants to confirm post-menopausal status only.

Investigators must document their review of each laboratory safety report.

After randomization, the sponsor study team and site will be blinded to HbA1c, FPG, and FPI measured by the central laboratory, unless the FPG meets the criterion for hypoglycemia as listed in Section 8.2.5.1, or indicates hyperglycemia with an FPG \geq 270 mg/dL (15.0 mmol/L).

10.3. Appendix 3: Adverse Events: Definitions and Procedures for Recording, Evaluating, Follow-up, and Reporting

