3.2.2.2. Hypoglycemic Monitoring

Hypoglycemia AEs will be recorded in the AE Case Report Form (CRF) with details of the event captured on the Hypoglycemic Event Details CRF. Details of when these will be recorded are given in the protocol Section 8.2.5.

For programming purposes, the hypoglycemic AE categories are based on the following:

- Severe Hypoglycemia: Severe is checked in the severity criteria of the CRF. This assessment will be made by the PI based on the protocol definition.
- Documented Symptomatic Hypoglycemia: If (1 Did the participant have symptoms of hypoglycemia?) Yes and (2 – Was the blood glucose measured?) Yes and result <70 mg/dL on the CRF, but hypoglycemia is not classified as severe.
- Asymptomatic Hypoglycemia: If (1) No and (2) Yes and result <70 mg/dL on the CRF, but hypoglycemia is not classified as severe.
- Probable Symptomatic Hypoglycemia: If (1) Yes and (2) No and (2b If blood glucose was not measured, did symptoms resolve when treated with carbohydrate or glucagon?) Yes on the CRF, but hypoglycemia is not classified as severe.

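### The glucose limit for severe hypoglycemia (Protocol 8.2.5.1, criterion 3) is printed as two values that are not equivalent: 54 mg/dL is 3.0 mmol/L, and 2.7 mmol/L is 48.6 mg/dL

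*Protocol*

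**What the plan says.** Protocol 8.2.5.1 defines a hypoglycemic adverse event (HAE) and then grades it. A severe grade needs every part of a three-part test: "In order to characterize the event as severe, all 3 criteria below must be met". Criterion 1 is inability to self-treat because of neurologic impairment. Criterion 2 is at least one listed neurological symptom. Criterion 3 has two branches. With a glucose measurement, the condition is "If blood glucose was measured and was ≤54 mg/dL (2.7 mmol/L) using glucometer (or central laboratory"). Without one, it is reversal by oral carbohydrate, glucagon or IV glucose, with no numeric limit. Everything else falls to a lower grade: "Events that do not meet all the criteria above for severe HAE are characterized as mild or moderate in severity".

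The protocol prints three other glucose limits in both units:

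- "a glucose value of <70 mg/dL (3.9 mmol/L") in the same section, for what counts as an HAE;
- "126 mg/dL (7 mmol/L") in exclusion criterion 23 (Section 5.2);
- "270 mg/dL (15.0 mmol/L") in Appendix 2 (Section 10.2).

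SAP 3.2.2.2 takes the severe category from the severity box on the CRF and says of it: "This assessment will be made by the PI based on the protocol definition". The documented symptomatic and asymptomatic categories both end with the condition "Yes and result <70 mg/dL on the CRF, but hypoglycemia is not classified as severe", and the probable symptomatic category also excludes severe events. SAP 6.3.1.7 lists the hypoglycemic events and summarizes them by treatment group.

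**The concern.** When glucose was measured, criterion 3 is a hard cut-off, and the protocol gives two cut-offs without a rule for choosing between them. An investigator reading in mg/dL and one reading in mmol/L could grade the same event differently, and an investigator who compares both figures cannot tell which governs.

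The SAP does not resolve this. It applies no glucose rule of its own to the severe category, and the remaining categories are defined by not being severe. Take a symptomatic event that meets criteria 1 and 2 and has a glucose between the two limits. It would be reported as Severe under one printed value and as Documented Symptomatic under the other, because every value in the band is below 70 mg/dL. Adverse-event incidence is a secondary safety endpoint. With very few such events expected, one regraded event would be visible in the severe row.

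**Working it through.** **Inputs.** The four glucose pairs printed in both units in the protocol: 70/3.9 and 54/2.7 (Section 8.2.5.1), 126/7 (Section 5.2) and 270/15.0 (Section 10.2).

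**Step 1: factor implied by each pair (mg/dL ÷ mmol/L).**

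| Pair | Implied factor |
|---|---|
| 70 / 3.9 | 17.95 |
| 126 / 7 | 18.0 |
| 270 / 15.0 | 18.0 |
| 54 / 2.7 | 20.0 |

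**Step 2: try to reproduce the printed mmol/L values with a factor of 18.**

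- 70 / 18 = 3.889, which rounds to 3.9, as printed.
- 126 / 18 = 7.0, as printed.
- 270 / 18 = 15.0, as printed.
- 54 / 18 = 3.0, where 2.7 is printed. This one does not reproduce.

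In the other direction, 2.7 × 18 = 48.6 mg/dL. Using 18.016 instead (an assumption, from a molar mass of glucose of about 180.16 g/mol) gives 54 / 18.016 = 2.997 mmol/L and 2.7 × 18.016 = 48.64 mg/dL, so the choice of factor makes no difference.

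**Step 3: could rounding explain it?** For 54 mg/dL to round to 2.7 mmol/L, the factor would have to lie between 54 / 2.75 = 19.6 and 54 / 2.65 = 20.4. At a factor of 18, only 2.65 × 18 = 47.7 to 2.75 × 18 = 49.5 mg/dL rounds to 2.7 mmol/L. Rounding is not the cause.

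**Step 4: size of the gap.** 54 − 48.6 = 5.4 mg/dL; 3.0 − 2.7 = 0.3 mmol/L. The disputed band is above 48.6 and up to 54 mg/dL.

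If mmol/L values are read to one decimal, 49 mg/dL (49 / 18 = 2.72) reads as 2.7 and meets both limits. The disputed whole values are then 50 (2.78), 51 (2.83), 52 (2.89), 53 (2.94) and 54 (3.00), or 2.8 to 3.0 mmol/L.

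**Step 5: effect on one event.** Suppose criteria 1 and 2 are met and glucose is 52 mg/dL (2.9 mmol/L). Against 54 mg/dL, 52 ≤ 54, so the event is severe. Against 2.7 mmol/L, 2.9 > 2.7, so it is not severe.

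**The case against.** The case for treating this as trivial has real content.

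- **Few events are exposed.** Section 8.2.5 does not expect hypoglycemia, and Section 5.2 excludes diabetes. In the two earlier Phase 2 studies (562 participants, 534 with T2DM and 28 without), one participant had severe hypoglycemia, and that participant had T2DM (Sections 2.2.2 and 2.2.2.1). The HAE definitions take glucose from a glucometer at the site or from the central laboratory. An impaired participant away from the site would probably fall in the branch with no measurement, which has no threshold.
- **No trial action was found that depends on the grade.** The discontinuation reasons in Section 7.1 and the dose-stopping example in Section 6.6.2 do not use HAE severity, and seriousness is defined separately from severity.
- **The CRF is not in the documents.** If it prints one consistent limit, sites may never meet the conflict.
- **The SAP works in mg/dL.** Its HAE categories use mg/dL only, and SAP 3.2.2.3.2 has a fasting plasma glucose alert of < 54 mg/dL.

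The first two points stand and limit the reach of the error. The third is a genuine unknown, but SAP 3.2.2.2 ties the investigator's assessment to the protocol definition, which is where the mismatch sits. The fourth does not settle the matter: the alert is a laboratory flag, not the severity criterion. None of these reconciles the two printed values.

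**Conclusion.** The concern holds. Criterion 3 is wrong as written, because its two figures cannot both be the limit. The text is current and legible, and nothing elsewhere in the protocol or SAP corrects it.

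The consequence is confined to grading HAEs that meet criteria 1 and 2 and have a measured glucose in the disputed band. An ordinary self-treated symptomatic event in the band is not severe under either value. The < 70 mg/dL limit that makes an event an HAE, the primary endpoint, the power and the error rate are unaffected.

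The conversion rests on the protocol's own pairs and needs no outside source. The narrower band of 50 to 54 mg/dL assumes that mmol/L values are read to one decimal, which the protocol does not state; the unrounded band is the firm one. That sites would actually apply different figures is an assumption, since the documents do not say which units each site reads. The error is small in reach but should be corrected, because it sits in an operative safety definition.

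**What to change.** The sponsor should reconcile the two figures in criterion 3 to one threshold, stated consistently in both units. No particular value is proposed here, and severity remains the investigator's three-part assessment. If the HAE form or its completion guidance repeats the mismatch, it should be corrected in the same way.

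In the hypoglycemic event listing already planned in SAP 6.3.1.7, check that any event with a measured glucose above 48.6 and up to 54 mg/dL was graded against the reconciled limit. This is best done before unblinding, so that no grade is revisited with treatment known.

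The cost is one corrected figure in the protocol and one check of an existing listing. Appendix 10 shows that the sponsor has used administrative clarification letters for comparable points. A CRF guidance change is needed only if the error is repeated there.
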